- Comparison of the following variables between the groups: granulation tissue integrity including hypergranulation state, time to close, flap/graft take, dehiscence, and reoccurrence.

Objective 2

To compare bacterial load, quantitative cultures, and clinical infections in wounds treated with NPWT PRO compared to wounds treated with NPWT PRO with simultaneous irrigation.

H1: Bacterial load measured with quantitative polymerase chain reaction (qPCR) will be progressively lower with continuous irrigation.

H2: Patients treated with simultaneous irrigation and NPWT PRO will have fewer infections defined by qPCR and clinical criteria.

Primary Endpoint:

- Comparison of reduction in bacterial load in wounds treated with NPWT and NPWT with simultaneous irrigation.

Secondary Endpoints:

- Comparison of incidence of infection in wounds treated with NPWT and NPWT with simultaneous irrigation.
- Infection-induced necrosis
- Infection reoccurrence post-closure

Objective 3

Assess changes in molecular markers associated with wound healing and regeneration of healthy tissue.

H1: NPWT PRO with simultaneous Irrigation will improve the levels of growth factors, cytokines, and other molecular markers over NPWT PRO alone.

H2: Negative pressure wound therapy will drive molecular changes in growth factors and other cytokines associated with regeneration of healthy tissue.

Primary Endpoint:

- To compare changes in genes and other molecular markers associated with wound healing between wounds treated with NPWT and NPWT with simultaneous irrigation.

Secondary Endpoint:

- To compare the addition of simultaneous irrigation on gene expression and expression of molecular markers from baseline.

Objective 4

Quality of Life and Patient Satisfaction Analyses

H1: Patients treated with the NPWT PRO device will show greater patient satisfaction with treatment than those treated with KCI Ultra NPWT therapy.

Primary Endpoints:

- To compare Quality of Life and Patient Satisfaction between patients treated with NPWT PRO versus patients treated with KCI Ultra NPWT therapy.
- To compare Quality of Life and Patient Satisfaction between patients with wounds treated with NPWT PRO versus NPWT PRO + SI.
- Evaluate functional status, using the Short Form 36 (SF36). These will be administered at baseline and at the last study visit.

Subjects and Recruitment

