We will enroll 90 patients from University of Texas Southwestern Medical Center and Parkland Hospital. The clinics that are part of the Parkland and University of Texas medical center include a racially and ethnically diverse patient population and are representative of those who suffer from type 2 diabetes, foot ulceration and risk of amputation.

Subject Stipend

\$35 per visit will be provided for research related visits (Up to a total of \$350).

Randomization

Subjects will be taken to the operating room for the initial debridement procedure of the wound. At the end of the procedure, subjects who continue to meet all inclusion and no exclusion criteria will be randomized in a 1:1:1 ratio to be treated with either PRO, PRO with simultaneous irrigation (PROI), or KCI Ulta NPWT. Prior to study initiation sealed prenumbered randomization envelopes will be provided to the research staff and used to obtain randomization assignment. Opening of the randomization envelop will occur intraoperatively at the conclusion of the initial surgical debridement of the wound and conformation of all eligibility requirements. Study staff will use the randomization number labels contained in the envelop. The number will become the subject ID. The assignment will be subjects randomized to PRO, PRO with simultaneous irrigation, or KCI Ulta NPWT.

The research staff will note treatment assignments on the intra operative randomization CRF and instruct the investigator. Treatment therapy wound dressings will be applied in the operating room or in the patient's room immediately after surgery per the investigators discretion, according to the manufacturer's recommendations. In order to ensure consistent study treatment, subjects will receive assigned treatment therapies within their study arm after the initial and any subsequent surgical debridements until the wound is deemed ready for closure or coverage by the Investigator. Subjects randomized to the PRO with simultaneous irrigation Treatment arm are the only subjects that will receive irrigation therapy at any time during the study treatment period. If irrigation therapy is discontinued, subjects in the Treatment arm will transition to PRO NPWT without irrigation. Subjects randomized to the PRO Control arm will receive NPWT only from the PRO therapy unit.

Eligibility Criteria

Inclusion Criteria

To be eligible for study enrollment, a subject must satisfy each of the following criteria:

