 - Untreated bone or soft tissue infection Any concomitant illness(es) or medical condition(s) that in the opinion of the investigator would render the subject not suited for study participation
 - Subject is taking a regimen of any medication(s) in a significant enough dosage that may affect chronic wound healing, including corticosteroid, chemotherapeutic and non-steroidal anti-inflammatory (NSAID) medications
 - Less than 18 years of age
 - Developmental disability/significant psychological disorder that in the opinion of the investigator could impair the subject's ability to provide informed consent, participate in the study protocol or record study measures, including untreated schizophrenia, bipolar disorder and psychiatric hospitalization within the last 2 years.
 - Females currently pregnant or planning pregnancy during the course of intended participation in the study
 - Active alcohol or substance abuse in the opinion of the investigator that could impair the subjects ability to provide informed consent, participate in the study protocol or record study measures.

Study Devices:

The Cardinal Health NPWT PRO system (K143016) continuous/intermittent vacuum-assisted drainage with simultaneous delivery of topical wound treatment solutions and suspensions over the wound bed. The systems are AC-powered, portable suction devices with battery backup that provide localized negative pressure when

used with the Cardinal NPWT Dressing to remove fluid and infectious materials from the wound. The systems are designed for patients who would benefit from a suction device, particularly as the device may promote wound healing, including patients who would benefit from vacuum assisted drainage and removal of infectious material or other fluids from wounds under the influence of continuous and/or alternating suction pressure. It is intended for use on patients with chronic, acute, traumatic, sub-acute and dehisced wounds, diabetic ulcers, pressure ulcers, flaps, grafts, and partial thickness burns. The Cardinal Health NPWT PRO systems provide care in the acute and extended clinical and home care settings.

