Subjects in the KCI arm of this clinical study will receive NPWT alone with the KCI USA, Inc. V.A.C.Via™ NPWT System (K132741) while residing at home. The V.A.C.Via NPWT System is a NPWT powered suction pump that consists of the following components: a sterile dressing system applied to the wound and connected via tubing to a therapy unit that generates negative pressure at the wound; and a sterile, disposable canister that collects wound exudates removed via the negative pressure. The V.A.C.Via™ NPWT System is intended for use as an integrated wound management system in acute, extended and home care settings. It is intended to create an environment that promotes wound healing by secondary or tertiary (delayed primary) intention by preparing the wound bed for closure, reducing edema, promoting granulation tissue formation and perfusion, and by removing exudates and infectious material. It is indicated for patients with chronic, acute, traumatic, subacute and dehisced wounds, partial-thickness burns, ulcers (such as diabetic, pressure or venous insufficiency), flaps and grafts.

Screening and Baseline Procedures

The following is a listing of all of the assessment and safety tools and evaluations to be used in this clinical study. For each study phase, the precise tools to be employed will be specified.

Ulcer History

- Type of wound: chronic or traumatic wound, sub-acute or dehisced wound, partial-thickness burn, ulcer (diabetic, pressure, etc.), flap, graft, other
- Duration since wound onset
- Wound location
- Previous wound history/amputation, if any

Medical Status

- The New York Heart Association (NYHA) Functional Classification System will be used to classify stage of heart failure.
 - The New York Heart Association (NYHA) functional classification system is used to classify the stage of heart failure from Class I to IV (as shown in the table below). This system relates symptoms to everyday activities and the patient's quality of life.

Class	Patient Symptoms
 None	No history of limitations
Class I (Mild)	No limitation of physical activity. Ordinary physical activity does not cause undue fatigue, palpitation, or dyspnea (shortness of breath).
Class II (Mild)	Slight limitation of physical activity. Comfortable at rest, but ordinary physical activity results in fatigue, palpitation, or dyspnea.

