The subject will record his or her current degree/level of pain for the study wound using the following 10-cm (100 mm) long Visual Analog Scale (VAS) labeled from '0': no pain to '100': worst pain imaginable

No pain 0 _____ 100 Worst Pain Imaginable

The VAS is the most commonly used scale for assessing pain [125]. The VAS is a simple scale that consists of a line anchored at one end by a label that indicates total absence of the measure being evaluated and at the other end by a label that indicates the worse imaginable presence of the measure being evaluated. The subject marks on the line the spot for the intensity of the measure, which is then measured using a ruler (in mm units).

In designing the VAS scale for this study, the standard guidelines for effective use of the VAS were followed, as listed below:

- The line should be 10, 15 or 20 cm long, as other lengths are less reliable.
- There should be a small vertical mark at each end, with numbers 0 and 100, and a verbal description.
- The verbal description must be in absolute terms (e.g. worst pain imaginable);
- The line itself should be clear of any markings and should be horizontal rather than vertical, for more reliable measurements.

Scales developed and used in the above way have been shown to be a proper ratio scale. Like a thermometer, this means that its two ends are rooted, and a doubling of the score does accurately reflect a doubling of the variable. Consequently, sensitive t-tests and ANOVA methods can be used in the analysis, so that significant differences can be identified with relatively small sample sizes or small differences between groups.

Infection Evaluation

Clinical Indicators

The following clinical indicators of significant bacterial infection will be recorded as present or absent for the study wound. 'Significant Bacterial Infection Clinical Indicators' are defined in this study as those presenting as excessive beyond which would typically be expected given the clinical condition and nature of the wound type.

- local heat
- spreading redness
- swelling
- increased purulent exudate (draining pus)
- odor
- cellulitis
- loss of function
- fevers
- chills

Swab Culture:

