If evaluation of the clinical indicators suggest the presence of significant bacterial infection of the wound, swab culture, utilizing swab technique [126] will be performed to confirm or reject the presence of significant bacterial infection severe enough to warrant the subject terminated from the study. The swab culture will be performed using a laboratory-provided swab that is pressed down over a 1 cm² area of the wound that is then delivered to the lab for analysis to determine Colony-Forming Units (CFUs) per gram of viable wound tissue and beta-hemolytic Streptococcus per gram of tissue. The findings of a positive or negative swab culture utilizing Levine's technique will be interpreted according to the following criteria:

- Positive culture indicating presence of bacterial infection: $\geq 1,000,000$ Colony-Forming Units (CFUs) per gram of viable wound tissue OR containing beta-hemolytic Streptococcus per gram of tissue at any level.
- Negative culture indicating absence of bacterial infection: $< 1,000,000$ Colony-Forming Units (CFUs) per gram of viable wound tissue OR no beta-hemolytic Streptococcus per gram of tissue at any level.

Tissue specimens will be obtained from the chronic wounds using 1) wound exudate, 2) broad Z-technique, and 3) Levine technique [126]. Acquisition of swab specimens was followed with a wound tissue biopsy. The diagnostic validity of each technique was determined by associating the quantitative culture findings of each swab specimen with the culture findings of concurrent tissue specimen (gold standard). Levine's technique performed best of the three swab techniques in terms of all four validity parameters: sensitivity was, specificity, positive predictive value, and accuracy.

Bio-burden

Bio-burden will be assessed using qPCR to quantify bacterial load from serial tissue specimens. Specific organisms that will be quantified using qPCR are listed in the table below. Bone, soft tissue will be sent to Research and Testing Laboratory (Lubbock, TX) for analysis.

Specific organisms (and two resistance factors) to be quantified using qPCR.			
E. faecalis	E. faecium	S. epidermidis	M. morgani
K. pneumonia	S. aureus	C. striatum	S. haemolyticus
S. agalactiae	S. marcescens	F. magna	S. mutans
S. pyogenes	H. influenzae	P. mirabilis	Vancomycin res.
C. albicans	M. catarrhalis	C. parapsilosis	Methicillin res.
P. aeruginosa	S. pneumoniae	A. baumannii	Total Bioburden

Osteomyelitis

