 - The subject will re-enter the therapy administration phase including the weekly or standard of care efficacy and safety evaluation test site visits and procedures.

Home Health Visits

The study therapy will only be given while the subject is in the hospital. If the subject's wound is not ready for closure during the hospital stay, the subject will continue NPWT at home. NPWT at home will be without irrigation. If the subject continues to receive NPWT after hospital discharge, the subject will be seen twice weekly by a home health nurse for dressing changes. The home health nurse will collect sitting blood pressure and pulse rate. Amount, type and character of wound drainage will be documented, as well as any adverse events and changes to concomitant medications. Offloading will be reapplied after dressing changes. At the same time, subject will continue to be followed by the study doctor during regular post-operative visits at outpatient clinic. If the wound closes, End of study visit will be performed and she/he will see the study doctor at outpatient clinic to have the closed wound checked.

Safety and Efficacy Evaluation

During the study therapy administration and evaluation phase, the subject will attend once weekly or standard of care test site visits, commencing at the end of Week 1 of therapy administration and ending at the weekly or standard of care visit where the wound is determined ready for surgical closure and the therapy administration process is complete.

- Weekly or standard of care Efficacy Evaluations
 - Digital Photography of the Study Wound
 - Wound Measurement (using a ruler and the eKare Insight System)
 - Granulation Tissue Estimation
 - Additionally, at the final week of efficacy evaluation test site evaluation, Subject Satisfaction with Study Procedure Outcome Evaluation will be performed.
- Weekly or standard of care Safety Evaluations
 - Safety Measures
 - Debridement Indication
 - Degree of Pain Rating
 - Infection Evaluation: encompassing swab culture and osteomyelitis assessment, if indicated.
- Inpatient Tissue Samples
 - Tissue samples will be taken and kept, for research, at inpatient study visits prior to wound closure for the following analyses.
 - For bacterial analyses
 - For gene expression analyses
 - After wound closure, no samples will be taken unless wound reoccurrence occurs.
 - Samples will be approximately 0.25-0.5 cm³ in size

- Bio-burden: qPCR evaluation
- Other Activities

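### Treated infections may enter the trial, but the plan does not say whether infection present at entry counts toward incidence of infection, and no clinical-indicator record is explicitly scheduled before the end of Week 1

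*Combined protocol and SAP*

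**What the plan says.** **Entry.** Under Exclusion Criteria the relevant item is "Untreated bone or soft tissue infection". Sepsis and fever above 101.5 are also excluded. A local infection already under treatment is not.

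**Endpoint.** Objective 2 lists as a secondary endpoint "Comparison of incidence of infection in wounds treated with NPWT and NPWT with simultaneous irrigation". Its hypothesis H2 expects "fewer infections defined by qPCR and clinical criteria" with irrigation. Neither place defines a new infection, and no qPCR cut-off is attached to the endpoint.

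**Clinical indicators.** The Infection Evaluation section lists nine signs, each recorded as present or absent, that must be "excessive beyond which would typically be expected given the clinical condition and nature of the wound type". If they suggest infection, a swab culture "will be performed to confirm or reject the presence of significant bacterial infection", at a severity that would justify ending the patient's participation.

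**Timing.** The tools are printed under Screening and Baseline Procedures, but the opening text there says "For each study phase, the precise tools to be employed will be specified". The only phase that names the Infection Evaluation is Safety and Efficacy Evaluation, with visits "commencing at the end of Week 1 of therapy administration". The Schedule of Events has no infection row. At entry it does mark Wound Assessment/Debridement (Screening and Day 0), culture and qPCR samples (Day 0), laboratory values (Screening) and current antibiotics (Screening and Day 0).

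**Randomisation.** "Opening of the randomization envelop will occur intraoperatively at the conclusion of the initial surgical debridement of the wound".

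**Analysis.** Survival Analyses Models plans ANOVA and repeated measures ANOVA of changes in quantitative cultures. No Day 0 covariate is named. Nothing in Biostatistics separates persisting from new infection.

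**The concern.** Infected wounds are plausible entrants. The preliminary data under Sample Size Justification come from inpatients whose lower-limb wounds were infected, and the Background calls infection very common in chronic diabetic foot ulcers.

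If such a wound still shows the indicators at the first timed evaluation, nothing in the plan says whether that is an endpoint event. A positive swab at that visit shows that infection is present then, not that it began after randomisation. The comparison could therefore combine two effects of irrigation: clearing an existing infection and preventing a new one. Both are legitimate questions, but a reader of one combined count cannot tell which was answered.

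Timing adds to this. Irrigation is given only in hospital, and the inpatient column of the schedule covers Week 1, possibly running into Week 2. The first timed checklist may thus fall near the end of irrigation. The trial is open-label, so a judgement made then is made with the arm known. One made before randomisation is not, and it cannot be recreated later.

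**Working it through.** **The plan's own figures.** The only sample size stated concerns wound closure: 60% vs 90% at 80% power, about 25 per group at two-sided alpha 0.10 and about 31 at 0.05. The printed formula gives 25 and 32, so it reproduces to within one patient. The documents give no infection rate, so every rate below is an assumption for illustration.

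**1. How mixing changes the risk ratio.** Let b be the share infected at entry, and pc and pt the share of those still counted as infected on treatment under PRO and under PRO with irrigation. Assume new-infection risks of 0.20 and 0.10 among those uninfected at entry (true ratio 0.50). Then

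- PRO: b × pc + (1 − b) × 0.20
- PRO with irrigation: b × pt + (1 − b) × 0.10

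| Assumption | PRO | With irrigation | Ratio |
|---|---|---|---|
| b = 0.1, pc = pt = 0.2 | 0.02 + 0.18 = 0.20 | 0.02 + 0.09 = 0.11 | 0.55 |
| b = 0.3, pc = pt = 0.4 | 0.12 + 0.14 = 0.26 | 0.12 + 0.07 = 0.19 | 0.73 |
| b = 0.7, pc = pt = 0.6 | 0.42 + 0.06 = 0.48 | 0.42 + 0.03 = 0.45 | 0.94 |
| b = 0.3, pc = 0.4, pt = 0.2 | 0.12 + 0.14 = 0.26 | 0.06 + 0.07 = 0.13 | 0.50 |
| b = 0.3, pc = 0.4, pt = 0.1 | 0.12 + 0.14 = 0.26 | 0.03 + 0.07 = 0.10 | 0.38 |

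If the swab confirms only half of the persisting cases, the three equal-persistence rows become 0.19 vs 0.10 (0.53), 0.20 vs 0.13 (0.65) and 0.27 vs 0.24 (0.89). Equal persistence dilutes the ratio, halved persistence leaves it unchanged, and stronger clearance enlarges the apparent effect.

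**2. Precision of new infection among those uninfected at Day 0.** With 90 patients randomised 1:1:1 there are 30 per arm, and m = 30 × (1 − b) are uninfected at entry. The 95% half-width of the risk difference is 1.96 × √((0.2 × 0.8 + 0.1 × 0.9)/m) = 0.98/√m.

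| b | m per arm | Expected events | Half-width |
|---|---|---|---|
| 0 | 30 | 6 vs 3 | about 18 points |
| 0.5 | 15 | 3 vs 1.5 | about 25 points |
| 0.7 | 9 | 1.8 vs 0.9 | about 33 points |

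The normal approximation is rough at these counts.

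**3. Day 0 covariate for bacterial load.** With equal variances σ² and correlation r between Day 0 and follow-up log load, a change score has variance 2σ²(1 − r), and the Day 0-adjusted value has σ²(1 − r²). The ratio is (1 + r)/2: 0.65, 0.75 and 0.85 at r = 0.3, 0.5 and 0.7 (assumed), a variance 15% to 35% smaller. This reads the planned ANOVA of quantitative cultures as the analysis of the bacterial-load endpoint. No other between-arm analysis of change in load is named.

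**The case against.** **A baseline judgement does exist.** Eligibility requires someone to decide whether there is untreated infection, sepsis or fever, and eligibility is confirmed again in the operating room. The Day 0 wound assessment may well include a look for infection. The Safety and Efficacy list is also not a full timetable: it starts wound measurement at the end of Week 1 too, yet the schedule marks imaging at Day 0. This stands in part. A reader might infer that nothing about infection is recorded at entry, and the documents do not support that. What is missing is an explicit instruction to complete the nine indicators before randomisation, and a rule for using the entry information.

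**The bar for a confirmed infection is high.** Signs must be excessive for the wound type, and the swab must reach 1,000,000 CFU per gram or grow beta-haemolytic Streptococcus. Few treated and debrided infections may persist to that level. This stands as a reason why the effect may be small. The documents do not settle it.

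**Randomisation protects the comparison.** It balances entry infection in expectation, so a count of all on-treatment infections in all randomised patients is a valid randomised comparison. This stands. A reader might infer that the endpoint is invalid, or that it is biased toward or against irrigation. The documents support neither. The problem is interpretation.

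**Incidence ordinarily means new events, and clearance is covered by the bacterial-load endpoint.** The ordinary meaning helps only if infections present at entry are recorded in a standard way. Load reduction is related to clinical resolution but is not the same thing.

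**The covariate is an efficiency preference.** Agreed: an analysis of change already uses Day 0 values. It is a gain in precision, not the repair of an error.

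**Conclusion.** The concern holds as a minor point about one secondary endpoint. Wounds with a treated infection may enter, no rule says whether that infection counts, and the clinical indicators are not explicitly scheduled before the end of Week 1. The entry records that are planned allow only partial separation, so the endpoint may mix persisting with new infection.

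The size is unknown. On the assumed rates the ratio runs from 0.38 to 0.94 around a true 0.50, which shows only that the effect could be negligible or large, in either direction. The documents do not show how many infected wounds will enter or how many infections will persist.

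A reader might also extend the doubt to the main results. That does not follow: the wound-volume comparisons do not use this endpoint. The covariate suggestion concerns the Objective 2 primary endpoint and stands separately. Its 15% to 35% variance saving rests on equal variances and correlations of 0.3 to 0.7.

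**What to change.** 1. **Record.** Complete the existing nine-item checklist on Day 0, before debridement and therefore before randomisation, and add it to the Schedule of Events. The cost is one short form per patient.

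2. **Endpoint wording.** Keep the count of all on-treatment infections, in all randomised patients, as the between-arm comparison. Beside it report, by arm and descriptively, (a) new infection among those uninfected at Day 0 and (b) persistence or resolution among those infected at Day 0. Do not count an infection arising after resolution of a Day 0 infection as incident: who is then at risk depends on treatment, since the arm that clears faster gains more time at risk. With so few events, no covariate-adjusted infection model is advised.

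   The cost is that the new-infection estimate is imprecise: a half-width of about 18, 25 or 33 points with 30, 15 or 9 per arm at risk. The all-infection comparison loses nothing.

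3. **Bacterial load (Objective 2 primary endpoint).** Use Day 0 log qPCR load as a covariate in place of the unadjusted ANOVA of changes. The samples are already planned, so the cost is analysis wording. It does not help patients with no follow-up tissue, which is taken only at inpatient visits before closure or at recurrence.
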